4.2.7 Follow-up for Early Terminated Subjects

In the event that a subject is eligible, enrolled, and randomized into the study but must early terminate either prior to the index procedure (AtriClip placement) or even after the index procedure; the subject will be followed for 30 days for safety purposes.

5.0 PROCEDURE

5.1 General Description

Individual centers and investigators will be selected based upon their expertise in the targeted structural heart disease procedures (non-mechanical Mitral Valve Repair/Replacement, Aortic Valve Repair/Replacement, and Coronary Artery By-Pass procedures) as well as proficiency in AtriClip placement.

The term index procedure refers only to the placement/non-placement of the AtriClip (dependent on randomization). All procedures leading up to and after the placement of the AtriClip are considered part of the structural heart procedure and are to be conducted under the discretion of the surgeon in accordance to the hospital's standard of care.

Transesophageal Echocardiography (TEE) with Doppler

Transesophageal echocardiography (TEE) with Doppler must be performed prior to any epicardial surgical intervention. The purpose of the TEE with Doppler is to assess for presence of thrombus. *If a thrombus is present in the left atrium or LAA*, the subject will not be enrolled or randomized into the study and no *AtriClip will be placed*.

The AtriClip LAA Exclusion System must be used only by properly trained and qualified medical personnel in accordance with the Instructions for Use (IFU). Failure to properly follow instructions may result in improper functioning of the device.

Study Number: CP2015-2 CONFIDENTIAL Page 22 of 48

If the subject continues to meet all study eligibility criteria (including intra-operative exclusion criteria), they will be enrolled and randomized. If the subject is randomized to the group to receive the AtriClip LAA Exclusion System placement, the following steps are performed:

Note: A recommended surgical technique is presented below. It is recognized that individual patient anatomic variation, surgical conditions, or surgeon preference may necessitate modifications to the outlined procedures. Regardless, surgeons must adhere to the AtriClip LAA Exclusion System sizing criteria, device selection, and device use instructions as outlined in the IFU.

[figure not shown]
5.2 Left Atrial Appendage (LAA) Exclusion (Index Procedure)

5.2.1 No AtriClip arm

If the subject is randomized to the no AtriClip arm, the left atrial appendage should be left intact with no management.

5.2.2 AtriClip arm

If the subject is randomized to the AtriClip arm, the left atrial appendage should be managed using the AtriClip LAA Exclusion System. The left atrial appendage is typically accessible and exclusion of the Left Appendage by the AtriClip is believed to introduce little time or risk to the primary operation. In the event that, the surgeon deems that the AtriClip device is not able to be utilized for left atrial appendage after randomization, because of anatomical limitations or that it is not feasible or safe to address the LAA, the appendage may be left intact. In the event that a subject is randomized but must early terminate before or after the index procedure; the subject will be followed for 30 days for safety purposes.

Post Index Procedure - Subject Assessment

To assess the subject status with regard to potential bleeding, assessments of hemoglobin and hematocrit shall be performed post index procedure per the hospital's standard of care.

Study Number: CP2015-2 CONFIDENTIAL Page 23 of 48

5.3 Post-Surgical Follow-up Anticoagulation Therapy

Subjects who are diagnosed with POAF during their postoperative course should be treated per the institution's standard of care and may include anticoagulation therapy.

The decision to administer anticoagulation therapy in the post-operative/follow-up setting is at the discretion of the Investigator/Institution taking into consideration, the subject's ability to safely initiate and sustain anticoagulation therapy.

The anticoagulants that may be used in medical management may include:

- Acenocoumarol
- Acetylsalicylic acid
- Apixaban
- Dabigatran
- Edoxaban
- Heparin
- Nadroparin
- Rivaroxiban
- Warfarin
- Other (to be specified)

These are the anticoagulants that may be utilized in medical management. The decision of which anticoagulant to use (if any) is left to the discretion of the Investigator.

6.0 IDENTITY OF STUDY DEVICES

The devices utilized for the study include:

AtriClip Gillinov-Cosgrove LAA Exclusion Systems which are indicated for the occlusion of the left atrial appendage, under direct visualization, in conjunction with other open cardiac surgical procedures. Direct visualization, in this context, requires that the surgeon is able to see the heart directly, without assistance from a camera, endoscope, etc., or any other viewing technology. This includes procedures performed by sternotomy (full or partial) as well as thoracotomy (single or multiple).

All medical devices used during this study are cleared for commercial distribution and are to be used in accordance with approved product labeling.

[figure not shown]
Device Description

When closed, the AtriClip applies uniform pressure over the length of the AtriClip to ensure consistent, reproducible, and secure exclusion of the LAA. The AtriClip is available in the following lengths to accommodate different sizes of LAA: 35 mm, 40 mm, 45 mm, and 50 mm.

The AtriClip was cleared under K093679. The frame assembly of the implantable AtriClip consists of two Nitinol (nickel titanium) springs connecting two opposing titanium tubes (core), which are covered with a Polyurethane elastomer. This assembly is covered with a knit braided polyester fabric, composed entirely of Polyethylene terephthalate (PET). The Nitinol springs are biased toward the closed position allowing the device to close in the absence of opposing forces (Figure 1). When closed, the AtriClip applies uniform pressure over the length of the AtriClip to ensure consistent, reproducible, and secure exclusion of the LAA.

Study Number: CP2015-2 CONFIDENTIAL Page 24 of 48

[figure not shown]

Figure 1

6.1 Product Accountability

The investigator will maintain control over and keep a complete device inventory record for all study devices received from AtriCure. All shipping record receipts received with the study devices will be maintained. All study devices that are used during each procedure will be documented.

Study Number: CP2015-2 Record: Clinical Study Protocol **Version date:** 15Feb2017/ Rev: H CONFIDENTIAL

[figure not shown]
Page 25 of 48

[figure not shown]

Study Number: CP2015-2 CONFIDENTIAL Page 26 of 48

[figure not shown]

Study Number: CP2015-2 Record: Clinical Study Protocol **Version date:** 15Feb2017/ Rev: H

CONFIDENTIAL

- 8.0 DATA MANAGEMENT AND INTEGRITY
- 8.1 Data Completion and Record Keeping
- 8.1.1 Source Documents

Source documents are documents on which information regarding subjects are first recorded. PI subject files or hospital records generally are the basis of source document information. This may include but is not limited to, original subject files, hospital/clinic records, original recordings/tracing, and digital images from automated instruments, X-ray films, and laboratory results.

Source documents must be retained by the PI as part of the subject's permanent medical record. The information in the source documents is used to complete the eCRFs. All information captured on the eCRFs should be completely and accurately supported in source documentation. Study Monitors will verify data reported on eCRFs with site source documents. Any additional information relevant to the study should be included in the source documents. In particular, any deviations from the study protocol or procedures should be recorded in the source documents. The PI will retain originals of all source documents, subject consent forms, and study data.

Study Number: CP2015-2 CONFIDENTIAL Page 29 of 48

8.1.2 Data Collection

An EDC system will be utilized by study site personnel to transfer study data from source records (medical records and/or source document worksheets) onto common eCRFs. This system is a web-based, secure electronic software application This system is designed, developed, and maintained in a manner that is compliant with national and international GCP data protection/data privacy and electronic record/electronic signature (e.g., 21 CFR Part 11) regulatory requirements. The platform software has been validated in accordance with 21 CFR Part 11, European Commission's Directive on Data Protection and US Safe Harbor Certification. Prior to being released for data entry, validation of the study level components (i.e. data entry screens, associated edit checks and work flow) will be conducted in accordance with approved user acceptance testing procedures. Access to this system will be controlled so that only authorized users will have the ability to enter into the system. The system is considered a closed system according to 21 CFR Part 11 Electronic Records; Electronic Signatures.

The EDC system will be used to facilitate the collection of all study data at the site. Designated site personnel will be responsible for entering subject data into the EDC system. All external and Sponsor internal users will be trained on the EDC application at a level dependent on their planned function.

An EDC digital User Manual will be available under the help menu within the EDC website to assist in the collection and entry of source data into the electronic casebook.

Investigative study sites will be asked to enter subject data into the eCRFs no later than 2 weeks from the time the subject was seen for their scheduled study visit.

Detailed description of the eCRF components are included in the eCRF Completion Instructions. These will be provided to the Investigators prior to initiating subject enrollment. The respective eCRFs must be fully completed for each subject and signed electronically.

Data collected during the clinical investigation for each subject will be maintained as accurately and completely as possible with entries into an electronic data capture system provided by AtriCure. The personal data recorded on all documents, including copy documents, and within the system will be regarded as confidential. The Investigator will be responsible for the timing, completeness and accuracy of the details entered within the electronic data capture system. All data entered in the database must have source documents in the subject's medical records.

Data will be entered into the electronic data capture system by members of the Investigational team who have received training in the use of the system. The system will generate data queries at the point of data entry based on validation checks defined by AtriCure. Such validation checks will primarily be focused on validation of key variables including selected subject demographics, appropriate value ranges and date checks. Resolution of the queries will be the responsibility of the Clinical Investigator and investigation team members. Following completion of all data queries on each eCRF, the Clinical Investigator will be responsible for reviewing and confirming agreement to the data within the system.

The Investigator must record the subject's participation in this clinical investigation in the subject's hospital notes. In addition, the Investigator must keep a separate list of all subjects entered into this clinical investigation showing each subject's name, date of birth and assigned subject number (for identification purposes). A subject Identification Log will be provided in the Investigator's File for this purpose.

Study Number: CP2015-2 **CONFIDENTIAL** Page 30 of 48

8.1.3 Data Correction

Corrections to eCRFs will be prompted via automated electronic edit checks and queries manually created by reviewers. The corrections and the individual making the correction(s) to the eCRF will be within EDC.

8.1.4 Investigator Regulatory Binder

Each Investigator must maintain an accurate, complete, and current copy of the Investigator Regulatory Binder. Upon receipt of copies of changes or revision updates to the Binder from the Sponsor, the Investigator will add the updated document to the Regulatory Binder. If an Investigator holds multiple copies of the Regulatory Binder, then all copies must be updated with the current revisions.

8.1.5 Study Correspondence

Each Investigator and all personnel from the investigational site will maintain records of all correspondence, electronic, written, and verbal, relating to any aspect of the clinical investigation. The records are maintained in the Investigator Regulatory Binder consisting of, but not limited to correspondence with other participating clinical investigators, the reviewing IRB, and the Sponsor. The CRA will examine the contents of the correspondence.

8.1.6 Data Privacy

Subjects will be made aware that their personal data will be collected and processed in accordance with data protection legislation including the Health Insurance Portability and Accountability Act of 1996 (HIPAA). Subjects will be asked to sign an Authorization for Release of Personal Health Information (PHI) for the purpose of this investigation. This authorization may be combined with the ICF depending on local IRB preference. Results from the Clinical Investigation may be published. However, subject confidentiality will be maintained at all times and it will not be possible to identify individual subjects from any data presented.

8.1.7 Record Retention, Inspection, and Custody

The PI must maintain all documentation related to the study until notified by the Sponsor. The PI will allow representatives of the Sponsor, IRB, the FDA, or other government regulatory agencies to inspect all study records, eCRFs, and corresponding portions of the subject's office and/or hospital medical records at regular intervals during the study. These inspections are to verify adherence to the protocol, integrity of the data being captured on the eCRFs, and compliance with applicable regulations.

Subject medical records will be kept confidential. Study reports will not identify subjects by name. These reports may be submitted to the FDA and/or regulatory authorities.

If custody of the records is transferred, notice of such a transfer should be given to the Sponsor no later than ten (10) working days after the transfer occurs.

The Investigator should retain copies of all documents pertaining to this clinical investigation (including source documentation, the informed consent document and any other documents to identify the subjects) for at least 2 years after this clinical investigation is completed. In addition, if the Clinical Investigator moves/retires, etc., he/she should provide AtriCure Inc. the name and address of the person who will look

Study Number: CP2015-2 CONFIDENTIAL Page 31 of 48

after and be responsible for the subjects' clinical investigation related records.

8.1.8 Medical Dictionary Coding

Medical dictionary coding will be performed using a coding thesaurus algorithm. The MedDRA will be used upon data entry and query resolution for AEs, SAEs, via automated and manual coding processes.

8.1.9 Data Quality Assurance

Quality control and quality assurance processes implemented during this study to ensure subject safety rights, and welfare are protected and to foster data integrity are characterized below.

8.1.10 Investigator Training - Protocol Specific Training

Protocol training will be scheduled once IRB approval is obtained and the Clinical Study Agreement is executed. AtriCure, Inc. will train the study site on the protocol and that training will be documented. It is ultimately the responsibility of the Investigator to ensure all clinical site personnel participating in this study are trained.

The index procedure may only be performed by qualified investigators, familiar with the study procedures and techniques.

8.1.11 Monitoring

This study will be monitored by the sponsor to ensure:

- The rights, safety and well-being of the subjects are protected;
- The reported study data is accurate, complete, and verifiable from source documents; and
- The conduct of the study is in compliance with the currently approved protocol/amendment(s), applicable GCPs, and with applicable local/regional regulatory requirements.

In order to perform the monitoring role effectively, the CRA must verify eCRF entries with source documents. The CRA must be given access to primary subject data which supports the information recorded on the eCRF, i.e. hospital notes, appointment books, original laboratory records, etc. Access to

Study Number: CP2015-2 **CONFIDENTIAL** Page 32 of 48

these documents must also be given should the regulatory authority in the instance of an external inspection. Since a subject has the right to refuse access to these documents on the grounds of confidentiality, consent to access is included in the informed consent document, which the subject signs.

The Principal Investigator will receive reasonable notification prior to each monitoring visit during the course of this clinical investigation. At each visit, the Principal Investigator will be expected to co-operate with the CRA for the review and verification of eCRFs and any additional records that may have been previously arranged between the Principal Investigator and the CRA.

8.2 Changes to Protocol, Protocol Deviations and Protocol Amendments

8.2.1 Changes to Protocol

The Investigator should not implement any deviation from, or changes to the protocol without agreement by the sponsor and prior review and documented approval/favorable opinion from the IRB of an amendment, except where necessary to eliminate an immediate hazard(s) to study subjects, or when the change(s) involves only logistical or administrative aspects of the study (e.g., change in CRA(s), change of telephone number(s)). In the event of an emergency situation, the Investigator must notify the CRA or AtriCure immediately. A full written report of the situation must be forwarded to the IRB who approved the original protocol and AtriCure within 10 working days of the event.

8.2.2 Protocol Deviations

The Investigator agrees to conduct the study in accordance with this protocol; however, protocol deviations may occur during the course of the study. Protocol deviations are events occurring during the conduct of the study which are not in compliance with the protocol and for which an amendment has not been granted. Protocol deviations can be committed by the Sponsor, the PI, or study subject. A deviation can be identified from a number of sources. Potential sources include, but are not limited to: a member of the PI's staff, the CRA during monitoring visits, or a member of the data management or statistical groups when entering or analyzing data. The PI or PI's representative are encouraged to contact the CRA or AtriCure as soon as possible upon observing a protocol deviation. Regardless of the source, it is crucial to document the deviation and record all corrective actions. Protocol deviations will be reported in the final report.

The process for capturing deviations will be detailed in the monitoring plan. The process will require that documentation describe the deviation, appropriate actions taken, and will be included in the study file for the respective PI and subject. The study site representative will be advised to record the deviation and relevant discussion with the Sponsor about the deviation in subject source documents.

Protocol deviations affecting the scientific soundness of the study or the rights, safety, or welfare of the subjects, will be reported by the PI, as required by the IRB.

Protocol deviations will be summarized and grouped into relevant categories for analysis and may include, but not be limited to, subjects who:

- Entered the study although they did not satisfy the eligibility criteria; or
- Developed withdrawal criteria during the study, but not removed.

Study Number: CP2015-2 **CONFIDENTIAL** Page 33 of 48

8.2.3 Protocol Amendments

If it becomes necessary to amend the protocol, then the nature of the amendment will be agreed between the Sponsor and the Principal Investigator(s) and this will be recorded with a justification for the amendment. The appropriate IRBs will be informed of amendments prior to implementation of the change.

9.0 STATISTICAL METHODS

9.1 Clinical Study Objective

The objectives of this study are to:

- 1. Compare impact of POAF among two randomized treatment arms; patients with POAF and surgical LAA closure (using AtriClip Gillinov-Cosgrove LAA Exclusion Systems) versus patients with POAF and no surgical LAA closure.
- 2. Evaluate Healthcare resource utilization [i.e. Hospital length of stay (LOS), emergency room and/or hospital re-admissions, and costs associated with specific adverse events that may be related to atrial fibrillation].
- 3. Evaluate long-term outcomes of LAA closure with AtriClip in patients at risk of developing POAF.

These patients will be enrolled prior to a scheduled existing cardiac procedure and randomized prior to the study index procedure (AtriClip placement). Perioperative event rates and postoperative outcomes including reoperation for bleeding, hospital length of stay, neurologic consults for stroke/TIAs, ED visits, and hospital readmissions through interval follow ups will be determined.

9.2 Study Endpoints

The following endpoints will be collected for this hypothesis generating pilot study:

- 1. Perioperative complications associated with AtriClip placement. [Defined as: stroke, major bleeding that requires re-operation and/or transfusion of > 2 U packed red blood cells (PRBC) within any 24-hour period during the first 2 days' post-index procedure, myocardial infarction (MI), or death.]
- 2. Intraoperative successful exclusion of LAA. [Defined as no (0 mm) flow between LAA and LA and < 5 mm LAA remnant by intraoperative TEE with Doppler.]
- 3. Composite event rates between the group of subjects diagnosed with POAF (AtriClip vs no AtriClip) through 365 days' post index procedure and between the group of subjects not diagnosed with POAF (AtriClip vs no AtriClip) through 30 days' post index procedure. Events to be evaluated include: Thromboembolic & Hemorrhagic Events such as cerebrovascular accident (CVA), transient ischemic attack (TIA), peripheral ischemia, hemorrhagic stroke, neurologic bleed, gastrointestinal (GI) bleeds, or other major bleeding event.
- 4. Composite event (listed above) rates through 365-days post index procedure for all AtriClip patients, regardless of whether the patient develops POAF.
- 5. Healthcare resource utilization variance between groups as related to the composite events above. [Specifically hospital length-of-stay (LOS), reoperation for bleeding, neurologic consults for stroke or TIA, emergency department (ED) visits, and hospital readmissions.]

[figure not shown]

9.3 Healthcare resource utilization

Healthcare resource utilization will be compared between groups. Major resource use collected at various study visits/follow-up calls will include hospital resources (OR time, LOS, etc.), cardiac related medication use, readmissions, including 30 days readmit, neurological consults, additional procedures during follow-up related to index procedures, and rehabilitation associated with post index procedure strokes. Costs from standard sources (DRGs, CPT codes, RedBook, published studies for SAE and Rehab, etc.) may be assigned to assess economic impact and summed over the 365-day treatment period to obtain total treatment costs.

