9.7.1 Effectiveness and Health Economic Analysis

A Pearson's Chi-Squared test will be used to compare the incidence of successful LAA exclusion between the two procedure groups. Alternatively, a Fisher's Exact test will be used if justified by small cell counts (less than 5) and Clopper-Pearson (Exact) 95% CI will also be reported.

In addition, LAA exclusion might also be analyzed using multiple logistic regression model with the proportion of the event of successful LAA exclusion as the dependent variable and the following independent variables: sites (or clusters of sites), surgical approach (sternotomy, right mini-thoracotomy or other), age, gender, CHA2DS2- VASc score, HASBLED score and relevant interaction terms.

Study Number: CP2015-2 CONFIDENTIAL Page 36 of 48

Healthcare resource use will be assessed by examining either total resource use, treatment costs or formal cost effectiveness/cost utility analysis. Resource use such as hospital length of stay, OR time, and total treatment costs will be compared between the treatment groups using a two-way analysis of variance (ANOVA) model with procedure group (AtriClip LAA Closure or anticoagulation therapy and without AtriClip LAA Closure) and site as fixed effects in the model.

These endpoints will also be compared using the two-sided t-test. A Shapiro-Wilk test of normality will be performed and if the normality assumption is not met, an approximate non-parametric model (e.g. Wilcoxon rank-sum test) may be performed.

A Pearson's Chi-Squared test will be used to compare difference in 30 day readmits, number of neurological consults, additional procedures, and patient medication use between the two procedure groups.

Formal economic models utilizing treatment effectiveness (Quality adjusted life years, costs to reduce stroke, etc.) may be built with collected data and other secondary sources accounting for specific country perspective and discounted appropriately.

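### Additional procedures are counted only if related to the index procedure, which Section 5.1 confines to placing or not placing the clip, so the planned between-arm test of this item can register almost nothing in controls

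*Combined protocol and SAP*

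**What the plan says.** Four parts of the protocol bear on this item.

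- **Collection (Section 9.3).** One of the listed resource items is "additional procedures during follow-up related to index procedures". Standard costs may be assigned to resource use and "summed over the 365-day treatment period to obtain total treatment costs".
- **Definition (Section 5.1).** "The term index procedure refers only to the placement/non-placement of the AtriClip (dependent on randomization"; the parenthesis and the sentence close there. The next sentence assigns the rest elsewhere: "All procedures leading up to and after the placement of the AtriClip are considered part of the structural heart procedure". Section 9.1 uses the term in the same sense: "study index procedure (AtriClip placement".
- **Control arm (Section 5.2.1).** In controls, "the left atrial appendage should be left intact with no management".
- **Analysis (Section 9.7.1).** A Pearson chi-squared test is to "compare difference in 30 day readmits, number of neurological consults, additional procedures, and patient medication use between the two procedure groups". Total treatment cost is compared by ANOVA and t-test.

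I found no rule for judging relatedness in a control subject, and no count of additional procedures regardless of relatedness.

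**The concern.** The filter works differently in the two arms. In the AtriClip arm, a later procedure counts if it is attributed to the clip. In the control arm, it counts only if someone attributes it to a clip not having been placed. The investigator making that judgement knows the assignment.

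The between-arm result for this item is then governed largely by how often clip-related procedures occur, not by how many additional procedures patients in each arm need. Objective 2 concerns resource use and the costs of events that may be related to atrial fibrillation. For that purpose, procedures avoided matter as much as procedures caused, and this item has almost no way to record procedures avoided.

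**Working it through.** The plan states no figure for this item, so there is none to reproduce. The check has two parts: tracing the term, then showing what the planned test does with the resulting count.

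**1. Tracing the term.** The filter is in 9.3, its meaning in 5.1 (repeated in 9.1), the control-arm content in 5.2.1 and the test in 9.7.1. Read together, a control procedure enters the count only if it is judged related to non-placement. A control count near zero is an inference from the definition; the documents do not state it.

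**2. Inputs for the illustration.**
- POAF population: 533 AtriClip and 267 control subjects (Section 9.4). Section 9.6 makes this population primary for health economic endpoints.
- All subjects: about 1333 and 667 (Section 9.4).
- Two-sided α = 0.05 (Section 9.7).
- Control count fixed at 0: assumption.
- Clip-related procedure rate of 0.5% to 3%: assumption. The documents give no rate.

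**3. Smallest significant count.** With k events among n₁ clip subjects, 0 among n₂ controls and N = n₁ + n₂, the uncorrected Pearson statistic reduces to

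χ² = N·k·n₂ / [n₁·(N − k)].

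- 533 vs 267, k = 8: 800 × 8 × 267 / (533 × 792) = 4.05, p = 0.044. At k = 7, χ² = 3.54, p = 0.060.
- 1333 vs 667, k = 8: 2000 × 8 × 667 / (1333 × 1992) = 4.02, p = 0.045. At k = 7, χ² = 3.51, p = 0.061.
- Fisher's exact test at k = 8 gives p = 0.057 and 0.058. At k = 9 it gives 0.033 and 0.034.

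So 8 events suffice for Pearson and 9 for Fisher, at either size.

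**4. Chance of reaching that count.** With the control count at 0, the chance of significance is P(X ≥ 9) for Fisher or P(X ≥ 8) for Pearson, with X ~ Binomial(n₁, p).

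| Assumed clip-related rate | POAF 533 vs 267, Fisher | All 1333 vs 667, Fisher |
|---|---|---|
| 0.5% | 0.2% | 23% |
| 1% | 9% | 92% |
| 2% | 74% | about 100% |
| 3% | 98% | about 100% |

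At 1%, the expected clip-arm counts are 5.33 (533 × 0.01) and 13.33 (1333 × 0.01). The Pearson chance at 1% in the POAF population is 17%. All-cause procedure rates do not enter any of these figures.

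**5. With the filter removed.** If all procedures are counted and both arms have an assumed all-cause rate of 5%, the test (Fisher where counts are small) rejects 4.8% of the time at 533 vs 267 and 5.0% at 1333 vs 667. That is the nominal level.

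**The case against.** **The term may have been meant more widely.** Section 9.3 uses a plural, and the ITT definition in Section 9.6 speaks of a surgical index procedure attempted in either group. The authors may have had the whole operation in mind. Section 9.7.1 also names additional procedures without repeating the filter, so carrying it over from 9.3 is an inference. This stands as evidence of inconsistent use, but it does not override the express restriction in 5.1, and the passages would still need to be reconciled.

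**Much of what matters is captured elsewhere.** This stands and limits the point. Endpoint 5 compares reoperation for bleeding, neurologic consults, ED visits and readmissions between groups, and Section 9.3 adds rehabilitation after stroke. Endpoint 5 ties its measures to the composite events, but none of these items is tied to the index procedure.

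**Stronger readings.** A reader might infer that the cost total sets clip-related cost against almost nothing in controls. It does not: OR time, length of stay, medication, readmissions, consults and rehabilitation enter without this filter, a control procedure performed during a readmission may enter through it, and costing is optional. A reader might also infer that the sign of the procedure comparison would reverse. That needs all-cause procedure rates, which the documents do not give.

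**Unseen material.** The 9.3 list may not be exhaustive, the eCRF completion instructions are a separate document (Section 8.1.2), and the schedule of assessments is not in the text I could read. All procedures may in fact be collected. The written rule would still need to say so.

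**Exploratory status.** The trial calls itself a hypothesis-generating pilot, and a detailed analysis plan may follow (Section 9.8). That lowers the stakes but does not make this comparison interpretable.

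**Conclusion.** The point holds for one item. Under the written definitions, the 9.7.1 comparison of additional procedures depends on the arm by construction, and a significant result could not be read as a difference in patients' need for further procedures. The effect on cost is confined to this item's share of an optional total.

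The size depends on an unknown rate. At an assumed 1% clip-related rate, a significant Fisher result is unlikely in the primary POAF population (about 9%) and likely in all subjects (about 92%); the larger figure should not be quoted alone, because it is not from the primary population. Both rest on a control count of exactly zero, which is the limiting case. The interpretive defect does not depend on either assumption.

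This should be corrected, but it does not threaten the trial's main clinical comparisons.

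**What to change.** - **Section 9.3:** replace the item with additional cardiovascular, neurological and bleeding-related procedures during follow-up, counted in both arms regardless of relationship to the index procedure.
- **Section 9.7.1 and any cost total:** use that count.
- **Window:** compare through 365 days in the POAF population, and through 30 days in non-POAF subjects or in all subjects. Section 4.1 provides 365-day follow-up for POAF subjects in both arms and for AtriClip subjects without POAF, but not for controls without POAF. A 365-day comparison in all subjects would therefore bring in a second asymmetry.
- **Clip-related procedures:** report descriptively for the AtriClip arm only, without a between-arm test.
- **Terminology:** reconcile the uses of index procedure in Sections 5.1, 9.1, 9.3 and 9.6.

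The cost is a wording change, slightly more data collection (how much depends on what the eCRF already holds), and some noise from procedures unrelated to the clip or to atrial fibrillation. Follow-up need not be extended if the windows above are used.
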